## **2.2 Study objectives and endpoints**

The primary and secondary efficacy objectives and safety objectives as well as endpoints of this study are as follows:

### **2.2.1 Primary efficacy objective**

The main efficacy objective is to assess the efficacy of Viaskin® Milk EPIT to desensitize milk-induced EoE in subjects at the end of the double-blind treatment period. The study will analyze the maximum esophageal eosinophil count on all specimens obtained at the end of the double-blind treatment period in esophageal biopsy after milk reintroduction in subjects with EoE. This is the gold-standard for the diagnosis of EoE.

### **2.2.2 Primary efficacy endpoint**

The primary efficacy endpoint is each patient's maximum esophageal eosinophil count on all specimens obtained from the biopsy at the end of double-blind treatment (visit 10), after milk reintroduction at visit 9.

### **2.2.3 Secondary efficacy objectives**

The secondary efficacy objectives are:

- a.** To describe the EoE symptoms score and global assessment score at end of each treatment period at 11 months (end of the double-blind treatment) and 22 months (end of the open-label treatment) in each treatment group and to determine if there

is a difference in improvement of the EoE symptom score between the active treatment group and the placebo group.

- b. To assess if there is a difference in the mean esophageal eosinophil count between the active treatment group and the placebo group at end of each treatment period at 11 and 22 months.
- c. To assess if the changes in mean and maximum esophageal eosinophil count from baseline to end of each treatment period at 11 and 22 months are different between the active treatment group and the placebo group.
- d. To assess if the percentages of subjects with  $\leq 1$  eosinophils/HPF (excellent response), subjects with 2-14 eosinophils/HPF (good response), and subjects with  $\geq 15$  eosinophils/HPF (poor response) at the end of each treatment period at 11 and 22 months are similar between the active treatment group and the placebo group.
- e. To assess if there is a difference in esophageal endoscopy score at the end of each treatment period at 11 and 22 months and to examine the changes in esophageal endoscopy score from baseline to the end of each treatment period at 11 and 22 months between the active treatment group and the placebo group.
- f. To examine the changes in the eosinophilic esophagitis quality of life score from baseline to the end of each treatment period at 11 and 22 months between the active treatment group and the placebo group.
- g. To examine the changes in the composite score, which will be calculated using four measures (Eosinophils/HPF, Esophageal Endoscopic Reference Score (EREFS), Pediatric Eosinophilic Esophagitis Symptoms Score (PEESS), and investigator assessment of EoE symptom activity), from baseline to the end of treatment period at 11 and 22 months between the active treatment group and the placebo group  
[Composite score = Maximum Eosinophils per HPF + 10\*EREFS + 2\*PEESS + 5\*  
(Investigator assessment of EoE symptom activity)].

- h. To assess if there is difference in time to development symptoms after milk reintroduction at month 9 and 20 between the active treatment group and the placebo group.
- i. To assess the changes in exploratory biologic markers including T-regulatory cells, thymic stromal lymphopoietin (TSLP), and complete blood count (CBC) with differential and milk-specific Immunoglobulin level and epigenetic changes between the active treatment group and the placebo group.

#### **2.2.4 Secondary efficacy endpoints**

The secondary efficacy endpoint measures are:

- a. The EoE symptom score and global assessment score at the end of each treatment period at 11 and 22 months (improvement in EoE symptom score will be defined as a decrease in total symptom score of two or more from baseline to the end of each treatment period at 11 and 22 months) as well as the change in EoE symptom score from baseline to the end of each treatment period at 11 and 22 months (e.g., the change in EoE symptom score at 11 month = the EoE symptom score at 11 month – (minus) the EoE symptom score at baseline, the change score is the difference) and the EoE frequency and severity symptom scores measured by Pediatric Eosinophilic Esophagitis Symptoms Score (PEESS) at the end of each treatment period at 11 and 22 months as well as the changes in these symptom scores from baseline to the end of each treatment period at 11 and 22 months.
- b. Mean esophageal eosinophil count which is the average of all of the samples obtained on biopsy at the end of each treatment period at 11 and 22 months.
- c. The changes in mean and maximum esophageal eosinophil count from baseline to the end of each treatment period at 11 and 22 months.
- d. The percentages of subjects with  $\leq 1$  eosinophil/HPF (excellent response), subjects with 2-14 eosinophils/HPF (good response), and subjects with  $\geq 15$

eosinophils/HPF (poor response) at the end of each treatment period at 11 and 22 months.

- e. Esophageal endoscopy score at the end of each treatment period at 11 and 22 months and the change in the esophageal endoscopy score from baseline to the end of each treatment period at 11 and 22 months.
- f. Changes in the eosinophilic esophagitis quality of life score from baseline to the end of each treatment period at 11 and 22 months.
- g. Changes in the composite score from baseline to the end of each treatment period at 11 and 22 months.
- h. Time to development symptoms after milk reintroduction at month 9 and 20.
- i. Changes in exploratory biologic markers, including T-regulatory cells, TSLP, and CBC with differential and milk-specific Immunoglobulin level and epigenetic changes.

#### **2.2.5 Safety objectives**

The safety objectives are to evaluate the safety of Viaskin® Milk EPIT treatment in children and adolescents with milk-induced EoE. Adverse events (AEs) and Serious Adverse Events (SAEs) by system organ class, severity, and relatedness to Viaskin® Milk, duration of local skin reactions induced by Viaskin® Milk, use of medications to treat AEs, systemic allergic symptoms and relatedness to Viaskin® Milk, changes in laboratory results, physical exams and vital signs will be assessed.

#### **2.2.6 Safety endpoints**

The safety endpoints are:

- a. Local skin tolerance: incidence, severity and duration of local Treatment-Emergent Adverse Event (TEAE) at site of Viaskin® application as reported by subjects in the diary card.

- b.** Potentially drug-related TEAEs.
- c.** Discontinuation due to TEAEs.
- d.** Laboratory data, physical examinations, and vital signs.
- e.** Systemic allergic symptoms and relatedness to Viaskin®.
- f.** Potentially drug-related systemic allergic symptoms.
- g.** SAEs.

### **2.3 Treatments**

Subjects will be randomized to receive Viaskin® with milk protein (500 µg of milk proteins) or placebo during the first year in the study. Viaskin® milk contains a dry deposit of natural milk protein formulated without adjuvant. The placebo treatment will consist of a similar formulation, but will be devoid of milk proteins. During the second year in the study (after third upper endoscopy), all subjects will receive open-label Viaskin® (500 µg of milk proteins).

### **2.4 Procedures**

Study subjects, randomization, replacements of the withdrawn subjects, and duration of the study are described.

#### **2.4.1 Study Population**

Pediatric subjects, aged 4 to 17 years, with milk induced Eosinophilic Esophagitis will be enrolled and randomized following confirmation of all eligibility criteria.

#### **Inclusion Criteria:**

1. Well documented symptoms suggestive of EoE after ingestion of milk and currently following a strict milk-free diet.

2. Upper endoscopy and biopsy at clinical evaluation during screening showing greater than or equal to 15 eosinophils per HPF isolated to the esophagus meeting the consensus diagnosis of EoE, after milk was re-introduced into the subject's diet (30 ml/day for 1 week to 2 months), while the subject was on a proton pump inhibitor.
3. Upper endoscopy and biopsy at clinical evaluation during screening showing 0 to 10 eosinophils per HPF isolated to the esophagus after a minimum of 6 weeks under a milk-free diet, and while the subject is on a proton pump inhibitor.
4. A negative pregnancy test for female subjects of childbearing potential. Females of childbearing potential must use effective methods of contraception to prevent pregnancy and agree to continue to practice an acceptable method of contraception for the duration of participation in the study.

#### **2.4.2 Randomization and replacement**

Approximately 22 eligible subjects to obtain 18 completed subjects will be randomized in a 3:1 ratio into two different treatment groups, (1) to receive EPIT with Viaskin® Milk (500 µg of milk proteins) or (2) placebo (16 subjects in the active Viaskin® Milk group and 6 subjects in the placebo group). Subjects who are withdrawn after beginning the treatment phase of the study will not be replaced. However, sufficient subjects will be included to ensure the minimum sample size.

#### **2.4.3 Study duration**

The planned duration of the clinical study is approximately 3 years (Start-up + Screening period + Treatment period + Closeout). Subject participation will be approximately 2 years (including up to 3 months and 2 weeks for the screening period; 11 months for the treatment period; 11 months for open label extension; and a 2-week follow-up visit). Recruitment into the study will stop when approximately 22 subjects have been

randomized to treatment. The study will be stopped when the last subject receiving the double-blind treatment completes the study or when the last ongoing subject has discontinued treatment, whichever occurs first.

## 2.5 Study visits

There are at least three visits during the screening period that will occur before enrollment and randomization to the active treatment phase of the SMILEE study. Fully eligible subjects will be required to attend 17 study visits as follows:

**Screening period:** Potentially eligible subjects will be enrolled into the study (Visit 1) to confirm Treatment Period study eligibility and obtain a number of study endpoints. The GI group will follow SOC procedures, but the dates of the first (Visit 2) and second (Visit 3) endoscopies with biopsies will not be mandated by the investigative team, but by the GI group for clinical care. The second upper endoscopy/biopsy will be done at a minimum of 6 weeks after milk-removal, per clinical care. If a patient meets eligibility criteria for the Treatment Period of SMILEE, s/he will be referred to the Allergy/Immunology division for continuation in the study. If the results of the first or second endoscopy with biopsies confirm ineligibility, the subject may be considered as screen failed and may not continue in the study.

Visit 1: Informed Consent obtained: milk introduction.

Visit 2: One week to 2 months after milk-introduction. Subjects have a SOC upper endoscopy/biopsy performed to confirm the diagnosis of EoE. Milk is removed from the diet.

Visit 3: Subjects have a second SOC upper endoscopy/biopsy to confirm milk induced EoE performed after a minimum of 6 weeks under milk-free diet.

If a subject has an endoscopy that confirms milk responsive EoE in the preceding 12 months, they will not need a repeat endoscopy to be eligible for the study.

**Treatment period:** There will be seven visits during the treatment period:

Visit 4 (Day 1): This visit corresponds to the first day of treatment and can be performed as soon as the results of the upper endoscopy and biopsy at Visit 3 are available and there is confirmed eligibility into the study.

Visit 5: This corresponds to day 8 of treatment.

Visit 6: This corresponds to month 1 of treatment.

Visit 7: This corresponds to month 3 of treatment.

Visit 8: This corresponds to month 6 of treatment.

Visit 9: This corresponds to month 9 of treatment (milk-reintroduction).

Visit 10: One week to 2 months after milk reintroduction. During this time, subjects will have weekly calls to monitor symptoms. Subjects have a third SOC upper endoscopy/biopsy. This is the end of double-blind treatment. The open-label treatment period will start on that day.

**Open label extension:** There will be six visits during the open-label treatment period:

Visit 11: This corresponds to day 8 after the Visit 10 research biopsy.

Visit 12: This corresponds to month 1 after the Visit 10 research biopsy.

Visit 13: This corresponds to month 3 after the Visit 10 research biopsy.

Visit 14: This corresponds to month 6 after the Visit 10 research biopsy.

Visit 15: This corresponds to month 9 after the Visit 10 research biopsy.

Visit 16: Subjects have a fourth upper endoscopy/biopsy. This is the end of open-label treatment period.

**Last assessment and end of study period:** There will be only one visit during this period.

Visit 17: This visit will be performed 2 weeks after Visit 16 for completers. This visit and assessment procedures have also to be performed for subjects prematurely withdrawn. This will be the End of Study Visit.

### **3. Statistical Considerations**

This section provides a detailed description of the statistical design, study objectives, and sample size determination and power calculation.

#### **3.1 Statistical design**

This is a randomized, double-blind, placebo-controlled clinical trial with Viaskin® Milk as Treatment 1 and placebo as Treatment 2. Primary and secondary efficacy objectives as well as the safety objectives are presented in Section 2.2.

#### **3.2 Sample size determination and power calculation**

The primary objective of this study is to determine whether mean maximum eosinophil counts is different in the subjects on the Viaskin Milk group compared to those on the placebo group. This is a pilot study in which we aim to identify efficacy of the Viaskin® Milk treatment. Sample size is based on projected subject volume. If efficacy is shown, our pilot data could be used to perform a power analysis for a larger study. We will recruit 38 subjects and plan to have 22 evaluable subjects with milk-induced EoE confirmed by endoscopy and biopsy. Approximately 20 subjects (15 subjects in the active Viaskin® Milk group and 5 subjects in the placebo group) will be randomized to two treatment groups to obtain 18 completed subjects assuming 10% dropout rate. This sample size will have 90% power to detect a difference of 40 in mean maximum eosinophil counts between the subjects receiving Viaskin® milk (mean maximum eosinophil count of 10) and the subjects on placebo (mean maximum

eosinophil count of 50) assuming a common standard deviation of 20 using a two group *t*-test with a two-sided significance level of 0.05.

### **3.3 Missing data**

Every attempt must be made by the Investigator to provide complete data. The primary analysis can be performed on data without imputation. However, exploratory analyses using various imputation techniques (i.e., last observation carried forward (LOCF)) will be utilized to assess the robustness of the data. Analyses of secondary efficacy measures will be based on the intent-to-treat (ITT) population with missing values imputed using the last value carried forward analysis.

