The rationale for up to 11 months of therapy (9 months off milk and up to 2 months after milk reintroduction) is based on preliminary data for IgE-mediated food allergy with efficacy being generally evaluated after 12 months of epicutaneous therapy (EPIT). In addition, the pre-clinical data in the pig model of eosinophilic gastritis was seen after around 3 months of therapy. It was extrapolated that between 9 to 11 months of EPIT in this pilot study, would be adequate. After the third endoscopy at the end of the double-blind treatment period (Visit 10), the study will be extended by one additional year and all subjects will receive open-label Viaskin® Milk (500 µg of milk proteins) for up to 11 months. A fourth endoscopy with biopsies for research will be done at the end of the open-label treatment period (Visit 16). The extension of the study will permit to assess the long-term safety and efficacy of Viaskin® Milk for up to 22 months of treatment in subjects with milk-induced Eosinophilic Esophagitis.

For EoE, there is no definitive treatment to mitigate disease progression of disease except for avoidance. In the standard of care, it is considered normal to periodically reintroduce foods to see if the subject has outgrown it. The first two endoscopies will be standard of care. The first endoscopy will permit to confirm the diagnosis of EoE and the second endoscopy will be used to confirm the diagnosis of milk-induced EoE. In our typical standard of care, the endoscopy will be performed, after treatment with proton pump inhibitor. The first endoscopy (standard of care) includes biopsy of esophagus, stomach and duodenum to ensure that eosinophilic inflammation is isolated to the esophagus. The second (standard of care), third (research) and fourth (research) endoscopies will include biopsies of esophagus only.

For safety purposes and to minimize risk, the first four patients will be 8-17 years old and after these patients are randomized, we will open the study to all ages 4-17 years old.

Table 2: Upper Endoscopies with Biopsies

1	Initial Endoscopy	Standard of Care	Biopsies of esophagus, stomach and duodenum
2	Second Endoscopy	Standard of Care	Biopsies of esophagus
3	Third Endoscopy (post double-blind treatment)	Research	Biopsies of esophagus
4	Fourth Endoscopy (post open-label treatment)	Research	Biopsies of esophagus

Study Visits:

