13.6.1 Missing Data

Every attempt must be made by the Investigator to provide complete data. The primary analysis can be performed on data without imputation. However, exploratory analyses using the multiple imputation method and last observation carried forward should be utilized to assess the robustness of the data.

Analyses of primary and secondary efficacy measures will be based on the intent-to-treat (ITT) population, with missing values imputed using the last value carried forward analysis.

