#### **4.4.2.3 Percentage of subjects per response rate**

The percentage of subjects showing an excellent response ( $\leq 1$  eosinophils/HPF), good response (2-14 eosinophils/HPF), and poor response ( $\geq 15$  eosinophils/HPF) at the end of the double-blind treatment and at the end of the open-label treatment as well as RR (i.e., the percentage of subjects showing excellent response in the treatment group divided by the percentage of subjects showing excellent response in the placebo group) along with 95% CIs between two treatment groups will be presented (*Table 13*).

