# Hodges-Lehmann estimate with 95% CI for median differences between two treatment groups will be reported.

### Table 12 specifications

Repeat with ITT population and PP population separately as Table 12A and Table 12B, respectively.

Table 13A. Summary Statistics for Response rate at the End of the Double-blind Treatment (Secondary Efficacy Endpoint)

	All	Viaskin® milk	Placebo	Relative Risk (95% CI)
Response rate, n (%)				
Excellent ( $\leq 1$ eosinophils/HPF)				
Good (2-14 eosinophils/HPF)				
Poor ( $\geq 15$ eosinophils/HPF)				
Values will be expressed as frequency counts (percentages).				

Table 13B. Summary Statistics for Response rate at the End of the Open-label Treatment (Secondary Efficacy Endpoint)

	All	Viaskin® milk	Placebo	Relative Risk (95% CI)
Response rate, n (%)				
Excellent ( $\leq 1$ eosinophils/HPF)				
Good (2-14 eosinophils/HPF)				
Poor ( $\geq 15$ eosinophils/HPF)				
Values will be expressed as frequency counts (percentages).				

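### Last-value carry-forward has no stop at Visit 10, so a child who leaves the open-label year can have a double-blind value reported as the 22-month result

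*SAP*

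**What the plan says.** SAP 3.3 puts secondary efficacy measures on the ITT population "with missing values imputed using the last value carried forward analysis". Protocol 13.6.1 extends the same rule to both levels of endpoint: "Analyses of primary and secondary efficacy measures will be based on the intent-to-treat (ITT) population", again with the last value carried forward. Neither text limits the rule to one treatment period.

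The measures covered include results at the end of the extension. SAP 2.2.4 defines the histological response categories at both time points, the last of them as "eosinophils/HPF (poor response) at the end of each treatment period at 11 and 22 months". SAP 4.4.2.3 presents them "at the end of the double-blind treatment and at the end of the open-label treatment". The shell for Table 13B, "Summary Statistics for Response rate at the End of the Open-label Treatment (Secondary Efficacy Endpoint", has All, Viaskin and Placebo columns and a relative risk. Tables 8, 9B, 12, 14 and 15 also report Visit 16 or end-of-open-label results by arm. SAP 4.1 groups ITT children by randomised treatment.

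Treatment changes between the two time points. SAP 2.3 states: "During the second year in the study (after third upper endoscopy), all subjects will receive open-label" active patches. Protocol 8.1 gives the purpose of this period: "The extension of the study will permit to assess the long-term safety and efficacy of Viaskin" Milk, over up to 22 months of treatment.

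**The concern.** Carry-forward is usually criticised for assuming that a child's state stays constant. Here it also crosses a change of treatment. A placebo-randomised child's Visit 10 biopsy was taken before any active patch, so it says nothing about the effect of open-label treatment. Entered at Visit 16, it would be read as the result after up to 11 months on the active patch.

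Milk exposure is a second issue. A child below 15 eosinophils/HPF at Visit 10 may stay on milk for up to 11 further months. If that child relapses and leaves without another biopsy, the pre-relapse value is carried and the child still counts as a good or excellent responder at 22 months.

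At stake are the two things the extension is meant to show: whether response lasts, and how children who cross over from placebo fare on active treatment.

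**Working it through.** The plan gives no figure for this point, so the check sets the schedule against the rule and then sizes one affected child.

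**Inputs**
- Arm sizes: 16 active and 6 placebo (Protocol 13.2, SAP 2.4.2); SAP 3.2 instead has 15 and 5.
- Visit schedule: Protocol Tables 3A and 3B and Section 9.
- Withdrawal procedures: Protocol 8.4.3.3 and 9.13.
- Drop-out: 10% in Protocol 13.2 and SAP 3.2; 22 randomised to 18 completed in both documents. No open-label rate is given.

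**Step 1. Which value would be carried?**

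| Measure | Scheduled after Day 1 | At Visit 17 / early termination | Last scheduled value for a child leaving between Visits 10 and 16 |
|---|---|---|---|
| Biopsy, endoscopy score | Visits 10, 16 | No | Visit 10 |
| Quality of life (PEESS is listed with it in Protocol Appendix 2 and is read here as following the same schedule) | Visits 10, 16 | No | Visit 10 |
| Composite (needs biopsy, endoscopy and PEESS) | Visits 10, 16 | No | Visit 10 |
| EoE symptom score | Visits 5 to 16 | Yes | A later open-label value |

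The problem therefore applies to the first three rows. The EoE symptom score largely escapes it. The primary endpoint is measured at Visit 10, so carrying a value past Visit 10 cannot touch it.

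**Step 2. Weight of one child in Table 13B**
- Placebo-randomised arm: 1/6 = 16.7 percentage points.
- Active arm: 1/16 = 6.25 percentage points.
- With the SAP 3.2 sizes: 1/5 = 20 and 1/15 = 6.7 points.

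**Step 3. How likely is at least one such child?** This needs an assumption. Suppose all 22 children enter the extension, leave independently, and do so at either of the plan's whole-study rates.
- At 10%: 22 × 0.10 = 2.2 leavers expected. The chance of at least one among 6 placebo-randomised children is 1 − 0.9^6 = 0.47.
- At 4/22 = 18%: 4.0 leavers expected. The same chance is 1 − (18/22)^6 = 0.70.

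These are illustrations, since both rates are borrowed from the whole study.

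**Step 4. Direction of the error**

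| Child who leaves after Visit 10 | Carried as | Effect on that arm's 22-month response rate |
|---|---|---|
| Placebo-randomised, ≥15, would have improved on active patch | Poor | Too low |
| Placebo-randomised, <15, would be ≥15 at 22 months | Responder | Too high |
| Active, ≥15, would have improved with longer treatment | Poor | Too low |
| Active, <15, relapses | Responder | Too high |

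The first and fourth rows favour the active arm; the second and third work against it.

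**Step 5. Does an observed-data analysis cure it?** Hypothetical active arm: 10 of 16 are responders at Visit 10, one of them relapses and leaves, and nobody else changes or leaves.
- True rate: 9/16 = 56.25%.
- Carry-forward: 10/16 = 62.5%.
- Observed data only: 9/15 = 60%.
- Leaver counted as non-responder: 9/16 = 56.25%.

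Observed data removes the placebo-period value but still overstates durability in this case. The non-responder analysis is needed beside it.

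**The case against.** Several points on the other side are sound.

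- **Relapse is partly covered.** The footnotes to Protocol Table 3 and Section 9.12.1 provide for telephone monitoring and a research endoscopy when symptoms recur. A relapsing responder may thus have a later biopsy to carry, so a reader who inferred that the rule erases relapse would go too far. What remains is the child who leaves without that endoscopy. Protocol 8.4.3.3 does not require one at withdrawal, and 9.12.1 ties it to recurrence after milk re-introduction, whereas a responder may never have stopped milk. None of this helps with the placebo-period value.
- **Carried values stay in the randomised arm's column.** One might infer that placebo-period disease is counted in the active-arm result. It is not. It sits in the Placebo and All columns and enters the between-arm estimate.
- **The shells point partly the other way.** Only the Table 7 specification mentions LOCF, and Tables 8, 12, 14 and 15 include a count of missing values, which suggests observed-data summaries. Table 13B has no such row, and a shell does not override the unqualified sentence in SAP 3.3. This conflict is itself a reason to clarify.
- **Longitudinal models.** SAP 4 foresees them for some efficacy endpoints but names none, so they do not displace the rule for the tables at issue.
- **Limited stakes.** These are secondary results in a 22-child pilot, without a concurrent placebo at 22 months, reported as estimates with intervals. That limits the weight of the point but does not remove it.

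**Conclusion.** The gap is real. As written, the rule enters a Visit 10 biopsy, endoscopy, quality-of-life, PEESS or composite value as the 22-month result for any child who leaves the open-label period without a later measurement. For placebo-randomised children that value precedes active treatment. Tables 8, 9B, 12, 13B, 14 and 15 are exposed. Each affected child moves a Table 13B percentage by up to 16.7 points in the placebo-randomised arm or 6.25 points in the active arm, given 6 and 16 children. How many would be affected is unknown, because no open-label drop-out rate is stated.

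Two stronger readings are not supported. The first is that the rule systematically favours the arm first given active patch, or always flatters durability. Step 4 shows errors both ways, so the net direction depends on who leaves. The second is a shift in the 22-month mean count of (50 − 10)/6 = 6.7 eosinophils/HPF per carried placebo child. That figure requires crossover children to reach a mean of 10, which the documents do not state for them, and it concerns a 22-month mean maximum count that has no table shell: Tables 6 and 7 stop at Visit 10.

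The primary analysis is unaffected. The wording should still be changed, because the correction is simple and the extension's main results depend on it.

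**What to change.** 1. In both SAP 3.3 and Protocol 13.6.1, state that values measured at or before Visit 10 are not carried forward to Visit 16. Changing only the SAP would leave the two documents in conflict.
2. Analyse Visit 16 biopsy, endoscopy, quality-of-life, PEESS and composite results on observed data, with the number missing by randomised arm. Add that row to Table 13B.
3. Beside Table 13B, report an analysis that counts children who leave before the Visit 16 biopsy as non-responders. Observed-only results can overstate durability, as Step 5 shows.

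The cost is wording in the SAP and a protocol amendment; visits, procedures and treatment do not change. The downside is a few fewer Visit 16 observations and a possibly less favourable 22-month response rate. The non-responder analysis may be pessimistic for children who leave for unrelated reasons, so it should be read together with the observed-data result.
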